## 9. STATISTICAL CONSIDERATIONS

Methodology for summary and statistical analyses of the data collected in this study is described here and further detailed in a SAP, which will be maintained by the sponsor. The SAP may modify what is outlined in the protocol where appropriate; however, any major modifications of the primary endpoint definitions or their analyses will also be reflected in a protocol amendment.

### 9.1. Estimands and Statistical Hypotheses

#### 9.1.1. Estimands

The estimands corresponding to each of the primary and secondary objectives are described in the table in [Section 3](#). The estimands to evaluate the immunogenicity objectives for NI are based on evaluable populations ([Section 9.3](#)). These estimands estimate the vaccine effect in the hypothetical setting where participants follow the study schedules and protocol requirements as directed. The estimand addresses the objective of estimating the maximum potential difference between the 2 compared groups, since the impact of noncompliance is likely to diminish the observed difference between the 2 groups. Missing serology results will not be imputed. Immunogenicity results that are below the LLOQ will be set to  $0.5 \times \text{LLOQ}$  in the analysis.

For safety evaluation, missing e-diary data will not be imputed. A partial missing AE start date (missing day or missing both day and month) will be imputed by assigning the earliest possible start date using all available information, such as the stop date of the AE and the vaccination date(s) from the same participant, following the Pfizer standard of handling incomplete AE start date. A complete missing start date for an AE is not allowed in the data collection. No other missing information will be imputed in the safety analysis.

#### 9.1.2. Statistical Hypotheses

##### 9.1.2.1. Noninferiority Comparing Pneumococcal Serotype-Specific OPA Titers 1 Month After Vaccination (Primary Endpoint)

NI of the immune response after vaccination for each serotype in 20vPnC is evaluated by serotype-specific OPA GMTs from the 20vPnC/saline group and the 13vPnC/PPSV23 group as described below.

Hypothesis testing will be used to assess NI of the serotype-specific OPA titers after administration of 20vPnC to those after administration of the control vaccine for each 20vPnC serotype. The null hypothesis for a serotype is

$$H_0: \ln(\mu_A) - \ln(\mu_B) \leq \ln(0.5)$$

where  $\ln(0.5)$  corresponds to a 2-fold margin for NI and

- $\ln(\mu_A)$  is the natural log of the geometric mean OPA titer 1 month after 20vPnC in the 20vPnC/saline group;
- $\ln(\mu_B)$  is the natural log of the geometric mean OPA titer 1 month after 13vPnC in the 13vPnC/PPSV23 group when the serotypes is one of the 13 shared serotypes (1, 3, 4, 5, 6A, 6B, 7F, 9V, 14, 18C, 19A, 19F, and 23F) or
- $\ln(\mu_B)$  is the natural log of the geometric mean OPA titer 1 month after PPSV23 in the 13vPnC/PPSV23 group when the serotype is one of the 7 additional serotypes (8, 10A, 11A, 12F, 15B, 22F, and 33F).

The null hypothesis will be rejected and NI of 20vPnC to the control vaccine for a serotype will be declared if the lower bound of the 2-sided 95% CI for the ratio of the GMT from the 20vPnC/saline group to that from the 13vPnC/PPSV23 group for that serotype is greater than 0.5 (2-fold criterion), with control being 13vPnC for the 13vPnC serotypes and PPSV23 for the 7 additional serotypes.

## 9.2. Sample Size Determination

Overall sample size of the study and the size from each country are based on considerations of the statistical probability of demonstrating NI of the overall immune response to 20vPnC comparing to control, a sufficient number of participants from each country for safety and immunogenicity evaluations to meet regulatory requirements of each country, and operational feasibility of the study.

Sample size and probability for the primary immunogenicity objectives are based on simulations of multivariate log-normal distributed random numbers with assumptions supported by Cohort 1 OPA results from the US pivotal Phase 3 study of 20vPnC (B7471007), as described in [Table 4](#).

Assuming the true GMRs and variance-covariance matrices for the 20 serotype-specific OPA titers are the same as that obtained from B7471007, the estimated probabilities to demonstrate NI for at least 18 out of 20, at least 19 out of 20, and for all 20 serotypes are approximately 99.3%, 94.7%, and 18.6%, respectively, assuming 630 evaluable participants in each group ([Table 5](#)). The large decrease in the probability of demonstrating NI for all 20 serotypes, compared to the probability of demonstrating at least 19 serotypes, is due to a relatively low observed GMR of 0.55 for serotype 8 in Study B7471007.

To ensure 630 evaluable participants per group for primary analysis, 700 participants per group (total 1400 participants) will be enrolled, assuming a dropout rate of about 10%.

A total of approximately 700 Japanese participants will be enrolled, and 500 and 200 participants will be enrolled from Korea and Taiwan, respectively.

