## Development of 20vPnC

The 20vPnC candidate is modeled after 7vPnC and 13vPnC. 20vPnC contains the polysaccharides of capsular serotypes present in 13vPnC and 7 additional capsular polysaccharides (for serotypes 8, 10A, 11A, 12F, 15B, 22F, and 33F) individually conjugated to CRM197. The 7 additional serotypes were selected based on their relative prevalence as a cause of IPD, their generalized geographic distribution, and other factors that would support inclusion, such as the presence of antibiotic resistance (11A, 15B), association with outbreaks (8, 12F), and greater disease severity (eg, meningitis, mortality) (10A, 11A, and 22F). These 7 serotypes have a long-standing association with serious pneumococcal disease and are responsible for a substantial burden of remaining pneumococcal disease.

The 20vPnC clinical development program in adults has included several trials, including 2 Phase 1 trials in healthy adults; 1 Phase 2 trial in adults 60 through 64 years of age; and 3 Phase 3 trials in adults  $\geq 18$  years of age.

In Phase 1 and Phase 2 trials, 20vPnC induced immune responses to the pneumococcal serotypes in the vaccine. The Phase 3 pivotal trial (B7471007) met its primary immunogenicity objectives of NI for all serotypes in common with licensed Prevenar 13 and 6 of the 7 additional serotypes when compared to PPSV23; 1 of the additional 7 serotypes (serotype 8) narrowly missed the statistical NI criteria; however, the serotype 8 immune response is expected to be similarly protective as the other 19 vaccine serotypes in 20vPnC,

based on OPA GMT, GMFR, proportion of participants with a  $\geq 4$ -fold rise in OPA titer, and proportion of participants with OPA titer  $\geq$  LLOQ. Secondary immunogenicity objectives for the immune responses from adults 18 through 49 and adults 50 through 59 years of age compared to those 60 through 64 years of age met NI for all 20 serotypes. This suggests that protective antibodies against all 20 serotypes were elicited by 20vPnC, and that protection against pneumococcal disease against the 13 common serotypes will be similar to 13vPnC, with the potential for protection against the 7 additional serotypes. The safety objectives were met in adults  $\geq 18$  years of age, demonstrating that the safety and tolerability of 20vPnC were comparable to licensed pneumococcal vaccines.

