## 3. OBJECTIVES, ESTIMANDS, AND ENDPOINTS

Objectives	Estimands	Endpoints
Primary Safety	Primary Safety	Primary Safety
To describe the safety profile of 20vPnC.	
In participants receiving at least 1 dose of study intervention and having safety follow-up after vaccination from each vaccine group:
 
 
• The percentage of participants reporting prompted local reactions within 10 days after the first vaccination (20vPnC or 13vPnC)
 
• The percentage of participants reporting prompted systemic events within 7 days after the first vaccination (20vPnC or 13vPnC)
 
• The percentage of participants reporting AEs within 1 month after vaccination with 20vPnC or 13vPnC
 
• The percentage of participants reporting SAEs within 1 month after vaccination with 20vPnC or 13vPnC
 
	
 
• Prompted local reactions (redness, swelling, and pain at the injection site)
 
• Prompted systemic events (fever, headache, fatigue, muscle pain, and joint pain)
 
• AEs
 
• SAEs
 

Primary Immunogenicity	Primary Immunogenicity	Primary Immunogenicity
To demonstrate that the immune responses to the 13 serotypes in 13vPnC (1, 3, 4, 5, 6A, 6B, 7F, 9V, 14, 18C, 19A, 19F, and 23F) induced by 20vPnC are noninferior to the immune response induced by 13vPnC.	In participants in compliance with the key protocol criteria (evaluable participants): 
 
For each of the 13 serotypes: GMR of serotype-specific OPA titers 1 month after 20vPnC to the serotype-specific OPA titers 1 month after 13vPnC
 
	
 
Serotype-specific OPA titers
 

To demonstrate that the immune responses to the 7 additional serotypes in 20vPnC (8, 10A, 11A, 12F, 15B, 22F, and 33F) induced by 20vPnC are noninferior to the immune response induced by PPSV23.	In evaluable participants: 
 
For each of the 7 additional serotypes: GMR of serotype-specific OPA titers 1 month after 20vPnC to the serotype-specific OPA titers 1 month after PPSV23
 
	
 
Serotype-specific OPA titers
 

Secondary Immunogenicity	Secondary Immunogenicity	Secondary Immunogenicity

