- GMRs and 2-sided CIs were calculated by exponentiating the mean differences of the logarithms of the titers (20vPnC/saline – 13vPnC/PPSV23) and the corresponding CIs (based on Student's t-distribution).

**Table 5. Probability of Demonstrating Noninferiority of 20vPnC to Control for OPA GMTs With Specified Overall Success Criteria**

Sample Size	Probability (%) With the Specified Overall Success Criterion a		
	≥18/20	≥19/20	20/20
600	99.1	93.5	18.2
630	99.3	94.7	18.6
650	99.6	95.1	18.0
700	99.8	97.4	19.7

Abbreviations: GMR = geometric mean ratio; GMT = geometric mean titer; OPA = opsonophagocytic activity.

Note: Probability is estimated based on 5000 simulated OPA results following multivariate log-normal distributions with mean vectors and variance-covariance matrices estimated from Study B7471007, with 1:1 randomization

a. Noninferiority for each serotype is defined by the lower bound of the 2-sided 95% CI for OPA GMR (20vPnC/saline group over 13vPnC/PPSV23 group) above 0.5.

CCI

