5. GENERAL METHODOLOGY AND CONVENTIONS

5.1. Hypotheses and Decision Rules

Hypothesis testing will be performed to assess noninferiority, comparing the 20vPnC/saline vaccine group against the 13vPnC/PPSV23 vaccine group for each of the 20 serotype-specific OPA titers.

A 2-fold margin will be used for each of the noninferiority hypothesis test.

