5.1.1. Hypothesis Testing

Hypothesis testing will be performed to assess noninferiority by comparing the serotype-specific OPA titers of the 20vPnC/saline group to those from the 13vPnC/PPSV23 group. The null hypothesis for each serotype-specific OPA titer is:

$$H_0: \ln(\mu_A) - \ln(\mu_B) \leq \ln(0.5)$$

where $\ln(0.5)$ corresponds to a 2-fold margin for the assessment of noninferiority.

- $\ln(\mu_A)$ is the natural log of the serotype-specific OPA GMT 1 month after 20vPnC administration for the 20vPnC/saline group.
- $\ln(\mu_B)$ is the natural log of the serotype-specific OPA GMT 1 month after 13vPnC administration for the 13vPnC/PPSV23 group when the endpoint is the serotype-specific OPA GMT from 1 of the shared 13 serotypes in 13vPnC, or,
- $\ln(\mu_B)$ is the natural log of the serotype-specific OPA GMT 1 month after PPSV23 administration for the 13vPnC/PPSV23 group when the endpoint is the serotype-specific OPA GMT from 1 of the 7 additional serotypes.

Noninferiority for serotype-specific OPA titers will be formally evaluated by a 2-sided 95% CI for the ratio of serotype-specific OPA GMTs (the 20vPnC/saline group to the 13vPnC/PPSV23 group) with results from 1 month after vaccination with 20vPnC (Visit 2) and 1 month after vaccination with 13vPnC (Visit 2) for the 13 matched serotypes. For the 7 additional serotypes, the GMR will be calculated for the ratio of serotype-specific OPA GMTs from the 20vPnC/saline group at Visit 2 to that from the 13vPnC/PPSV23 group at Visit 3. Noninferiority for a serotype will be declared if the lower bound of the 2-sided 95% CI for the ratio of $\text{GMT}_{20vPnC/\text{saline}}$ to $\text{GMT}_{13vPnC/\text{PPSV23}}$ for that serotype is greater than 0.5 (2-fold criterion).

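### Does the plan need a stated number of serotypes that must pass before primary objective 2 counts as met, given that serotype 8 will probably miss?

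*Protocol*

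**What the plan says.** Protocol 3 words the second primary immunogenicity objective as follows: "To demonstrate that the immune responses to the 7 additional serotypes in 20vPnC" are noninferior to those after PPSV23. The estimand beside it is a GMR for each of the seven serotypes separately.

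Protocol 9.1.2.1 sets one null hypothesis per serotype. The limit of ln(0.5) "corresponds to a 2-fold margin for NI", and the decision for a serotype rests on whether "the lower bound of the 2-sided 95% CI for the ratio of the GMT from the 20vPnC/saline group" to that from the control group exceeds 0.5. SAP 5.1 describes the testing as "comparing the 20vPnC/saline vaccine group against the 13vPnC/PPSV23 vaccine group for each of the 20 serotype-specific OPA titers". SAP 5.1.1 repeats the rule: "Noninferiority for a serotype will be declared if the lower bound of the 2-sided 95% CI for the ratio of" the two GMTs is above 0.5. SAP 6.1.2.1 then plans model-based GMTs, GMRs and 95% CIs by serotype, and a forest plot of all 20.

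Two places use wider language. Protocol 9.2 names "the statistical probability of demonstrating NI of the overall immune response to 20vPnC comparing to control" as one basis for the sample size, beside country requirements and feasibility. The columns of Table 5 stand under the heading "Probability (%) With the Specified Overall Success Criterion" and cover at least 18/20, at least 19/20 and 20/20. At 630 per group these are 99.3%, 94.7% and 18.6%.

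The introduction (Development of 20vPnC) says that the earlier pivotal trial "met its primary immunogenicity objectives of NI for all serotypes in common with licensed Prevenar 13 and 6 of the 7 additional serotypes". The same sentence adds that serotype 8 narrowly missed the criterion.

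**The concern.** An objective phrased as a demonstration, and a power table built on overall success criteria, suggest that someone will eventually declare objective 2 met or not met. No visible text says how. Two readings seem possible. The objective names seven serotypes, which suggests that all seven must pass. The account of the pivotal trial can be read as calling the objective met with six.

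The gap would be harmless if the readings nearly always agreed. Under the sponsor's own assumptions they usually disagree, because one serotype has a true ratio assumed to lie just above the margin. If the label were chosen after the serotype 8 result was known, a primary objective could be called met or not met on the same data.

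**Working it through.** **Inputs.** Table 4 gives GMTs, 95% CIs and n by serotype and group. Protocol 9.2 gives 630 evaluable per group. The margin is 0.5 with a two-sided 95% CI. The correlation between serotypes is not printed, so I assume a common value between 0 and 0.7.

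**SDs on the natural-log scale**, from SD = ln(upper/lower) / (2 × 1.9616) × √n, for serotype 8:
- 20vPnC/saline: ln(591.0/493.9) / 3.9232 × √1374 = 1.696
- 13vPnC/PPSV23: ln(1066.8/896.8) / 3.9232 × √1319 = 1.607

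**Power for one serotype** = Φ[ln(GMR/0.5)/SE − 1.96], with SE = √[(s₁² + s₂²)/630]. For serotype 8:
- GMR = 540.2/978.1 = 0.5523, and ln(0.5523/0.5) = 0.0995
- SE = √[(1.696² + 1.607²)/630] = 0.0931
- Power = Φ(0.0995/0.0931 − 1.96) = 18.6%

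The same formula gives 97.0% for 6A and 98.0% for 23F, the lowest values among the matched serotypes. It gives more than 99.9% for each of the other six additional serotypes.

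**Reproducing Table 5 at 630 per group** (200,000 simulated trials for each correlation):

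| Criterion | Table 5 | Correlation 0 / 0.3 / 0.5 / 0.7 |
|---|---|---|
| ≥18/20 | 99.3% | 99.9 / 99.5 / 99.2 / 98.9% |
| ≥19/20 | 94.7% | 95.1 / 94.7 / 95.0 / 95.6% |
| 20/20 | 18.6% | 17.5 / 18.3 / 18.5 / 18.5% |

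The printed figures are sound. Their Monte Carlo standard error at 18.6% is √(0.186 × 0.814/5000) = 0.55 percentage points.

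**Objective 2 under the two readings.** All 7: about 18.6%. At least 6 of 7: above 99.9%. They disagree when serotype 8 alone fails among the seven, with probability 100 − 18.6 = 81.4%. If the covariates in the primary model explain 10% to 50% of the variance (an assumption), serotype 8 power is 20.2% to 32.7%, so the readings disagree in 79.8% to 67.3% of trials.

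**What the protocol already shows.** Exactly 19/20 has probability 94.7 − 18.6 = 76.1%. The simulated probability that serotype 8 is the only failure among all 20 is 76% to 77%. Protocol 9.2 attributes the drop to the serotype 8 ratio of 0.55. The printed 20/20 figure and the computed 7/7 figure agree at 18.6%, so a separate 7/7 column would tell the reader almost nothing new.

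**What would change under a count rule.** The table takes each planned element in turn.

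| Element | Where | Depends on a count of serotypes? |
|---|---|---|
| Null hypothesis and decision | Protocol 9.1.2.1; SAP 5.1, 5.1.1 | No, one serotype at a time |
| Estimand | Protocol 3; SAP 2.1 | No, a GMR for each serotype |
| Reported results | SAP 6.1.2.1 | No, 20 GMRs with CIs |
| Secondary objectives | Protocol 3 | No, descriptive |
| Interim analysis | Protocol 9.5 | None planned |

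No gatekeeping or passing of alpha is visible. Each serotype conclusion keeps its one-sided 2.5% level whatever label the objective receives.

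**The case for a change.** The strongest case for a change is this. These are primary objectives, SAP 5.1 carries decision rules in its title and shows no redaction, and the likeliest single result is the one on which the readings differ. The choice also bears on error control. Requiring all seven needs no multiplicity adjustment, whereas a rule of at least six, with two serotypes exactly at the margin and independent (an assumption), could reach 1 − 0.975² = 4.9% one-sided. The remedy is a few sentences and adds no participants.

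Part of this stands. The word overall in Protocol 9.2 and Table 5 has no visible definition, and a sentence stating that conclusions are drawn by serotype would do no harm.

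The rest is weaker than it looks. The reading of six out of seven has no source in this trial's own rules. It comes from a sentence about a different study, and that sentence goes on to say that serotype 8 missed. Protocol 2.2.1 likewise reports noninferiority for six of seven and then treats serotype 8 separately. Both passages show how a miss is reported; neither sets six as the threshold for success. The 4.9% would arise only under a rule that the plan does not visibly adopt. Redacted text also follows the noninferiority rule in the synopsis and follows Table 5, so an omission cannot be established.

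**Conclusion.** No change to the plan is needed. Followed as written, it yields 20 prespecified noninferiority conclusions, each valid at one-sided 2.5%, and a report that shows serotype 8 as having passed or missed. A reader of that report needs no count rule to see what was demonstrated.

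The arithmetic behind the worry is right: at 630 per group serotype 8 passes with probability about 18.6%, or up to 32.7% if covariates explain half the variance, and two hypothetical labels for objective 2 would differ in about 67% to 81% of trials. But this is the probability that serotype 8 alone misses among the seven, which Protocol 9.2 in effect already discloses. It measures no error in the analysis.

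The conclusion rests on the visible text, in which no test is conditional on an objective-level verdict, and on the Table 4 ratios and variances carrying over to this trial.

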**Table 4. OPA GMT and GMR Results After Vaccination for Study B7471007 (Cohort 1)**

Vaccine Group (as Randomized)									
ST	n a	20vPnC/Saline			13vPnC/PPSV23			Vaccine Comparison	
		GMT b	(95% CI b )	n a	GMT b	(95% CI b )	GMR c	(95% CI c )	
1	1430	150.9	(138.3, 164.6)	1419	186.1	(170.6, 202.9)	0.81	(0.72, 0.92)	
3	1415	43.6	(40.9, 46.5)	1411	50.4	(47.2, 53.7)	0.87	(0.79, 0.95)	
4	1415	644.5	(584.3, 710.8)	1409	766.8	(695.5, 845.4)	0.84	(0.73, 0.97)	
5	1418	101.8	(93.6, 110.9)	1395	123.6	(113.4, 134.6)	0.82	(0.73, 0.93)	
6A	1403	1020.7	(921.8, 1130.2)	1390	1344.1	(1215.1, 1486.7)	0.76	(0.66, 0.88)	
6B	1413	1261.1	(1144.8, 1389.3)	1401	1542.6	(1399.1, 1700.9)	0.82	(0.71, 0.94)	
7F	1409	1056.7	(976.5, 1143.5)	1391	1250.2	(1154.0, 1354.4)	0.85	(0.76, 0.95)	
9V	1399	1668.1	(1526.1, 1823.2)	1391	1761.2	(1610.5, 1926.0)	0.95	(0.83, 1.07)	
14	1418	762.3	(697.2, 833.5)	1408	797.0	(731.7, 868.1)	0.96	(0.85, 1.08)	
18C	1420	1383.9	(1254.1, 1527.2)	1403	1653.2	(1497.3, 1825.4)	0.84	(0.73, 0.96)	
19A	1420	588.0	(540.9, 639.2)	1398	733.3	(673.5, 798.5)	0.80	(0.71, 0.90)	
19F	1421	297.2	(271.7, 325.0)	1403	367.4	(334.0, 404.1)	0.81	(0.71, 0.92)	
23F	1424	308.9	(273.2, 349.3)	1409	362.0	(320.0, 409.5)	0.85	(0.72, 1.02)	
8	1374	540.2	(493.9, 591.0)	1319	978.1	(896.8, 1066.8)	0.55	(0.49, 0.63)	
10A	1310	2257.2	(2059.8, 2473.5)	1263	1221.7	(1100.1, 1356.8)	1.85	(1.61, 2.12)	
11A	1198	5268.9	(4807.3, 5774.9)	1209	2932.8	(2673.3, 3217.5)	1.80	(1.58, 2.05)	
12F	1294	3191.6	(2895.2, 3518.3)	1222	2244.7	(1994.9, 2525.8)	1.42	(1.22, 1.66)	
15B	1283	2722.7	(2433.0, 3046.8)	1249	899.2	(786.3, 1028.3)	3.03	(2.54, 3.61)	
22F	1274	4588.5	(4141.3, 5084.0)	1227	2264.4	(2013.4, 2546.7)	2.03	(1.73, 2.37)	
33F	1157	6126.9	(5585.0, 6721.5)	1201	4345.7	(3955.6, 4774.1)	1.41	(1.24, 1.61)	

Abbreviations: CSR = clinical study report; GMR = geometric mean ratio; GMT = geometric mean titer; LLOQ = lower limit of quantitation; OPA = opsonophagocytic activity; ST= serotype.

Note: Assay results below the LLOQ were set to  $0.5 \times$  LLOQ in the analysis. OPA GMTs and GMRs were obtained from the B7471007 CSR.

- n = Number of participants with valid and determinate OPA titers for the specified serotype.
- GMTs and 2-sided CIs were calculated by exponentiating the mean logarithm of the titers and the corresponding CIs (based on Student's t-distribution).
- GMRs and 2-sided CIs were calculated by exponentiating the mean differences of the logarithms of the titers (20vPnC/saline – 13vPnC/PPSV23) and the corresponding CIs (based on Student's t-distribution).

**Table 5. Probability of Demonstrating Noninferiority of 20vPnC to Control for OPA GMTs With Specified Overall Success Criteria**

Sample Size	Probability (%) With the Specified Overall Success Criterion a		
	≥18/20	≥19/20	20/20
600	99.1	93.5	18.2
630	99.3	94.7	18.6
650	99.6	95.1	18.0
700	99.8	97.4	19.7

Abbreviations: GMR = geometric mean ratio; GMT = geometric mean titer; OPA = opsonophagocytic activity.

Note: Probability is estimated based on 5000 simulated OPA results following multivariate log-normal distributions with mean vectors and variance-covariance matrices estimated from Study B7471007, with 1:1 randomization

a. Noninferiority for each serotype is defined by the lower bound of the 2-sided 95% CI for OPA GMR (20vPnC/saline group over 13vPnC/PPSV23 group) above 0.5.

CCI

### 9.3. Analysis Sets

For purposes of analysis, the following analysis sets are defined:

Population	Description
Enrolled	All participants who have a signed ICD.
Randomized	All participants who are assigned a randomization number in the IWR system.
Evaluable 13-matched immunogenicity	All eligible randomized participants who receive the first vaccine as randomized, have Visit 2 blood collection within an appropriate window for Visit 2, have at least 1 valid OPA titer for any of the 13 matched serotypes at Visit 2, and have no other major protocol deviations as determined by the clinician.
Evaluable 7-additional immunogenicity	All eligible randomized participants who receive the assigned study interventions at Visit 1 for the 20vPnC/saline group or receive the assigned study interventions at both Visit 1 and Visit 2 for the 13vPnC/PPSV23 group, have either Visit 2 blood collection for the 20vPnC/saline group or Visit 3 blood collection for the 13vPnC/PPSV23 group within appropriate windows for Visit 2 or 3, respectively, have at least 1 valid OPA titer for any of the

Population	Description
	7 additional serotypes at either Visit 2 for the 20vPnC/saline group or Visit 3 for the 13vPnC/PPSV23 group, and have no other major protocol deviations as determined by the clinician.
CCI [REDACTED]	[REDACTED]
Safety	All participants who receive at least 1 dose of the study intervention with safety follow-up after any vaccination.

